Statistical Analysis Plan

September 15, 2015

Optimizing PrEP Uptake & Adherence Among Male Sex Workers (MSW)
Using a 2-stage Randomization Design
(NCT03086057)

Specific Aim 2: Pilot RCT. Initially, the distribution of all variables will be assessed, as will the autocorrelations across time between all study variables and the primary outcomes. Dependent variables will be examined to determine which distributional models are most appropriate for subsequent statistical procedures. We will examine the equivalence of the random assignment of groups with regards to key baseline characteristics, including socio-demographics and sexual risk-related variables. In the unlikely event that randomization does not work to balance these characteristics at baseline, we will assess whether baseline differences may account for differences in outcomes. Attrition effects will be evaluated by testing whether systematic differences exist between those participants who complete the research versus those who drop out. In this way, we can determine the nature of the potential bias introduced by attrition from the study.

Primary Analysis. The primary analysis for Stage 1 will compare PrEP initiation at 1-month post Stage 1 randomization between the study arms. For stage 2, the primary analysis will compare adherence (defined by percent of drug in blood) at the 3 and 6 month visits between the study arms. Changes in self-reported adherence, sexual behavior adjustment and substance use will also be examined. Moreover, group differences in number of PrEP clinic appointments kept will be compared. All analyses will use two-tailed tests of significance, with significance at alpha = 0.05. We will use generalized linear models (GLM) with properly-chosen link functions to analyze longitudinal data for each analysis. The GLMs will be estimated using generalized estimating equations with robust standard error estimates (GEE)^{67,68}, which provides an extension of regression analysis to the case of correlated or repeated observations and allows for inclusion of both categorical and count dependent variables and for appropriate modeling of covariance structures when observations are correlated across time. We will follow an intent-to-treat model, analyzing participants in the study arm to which they were assigned, regardless of fidelity to assigned group.

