Mediation analysis. If the intervention does achieve adherence in significantly greater magnitude than the comparison condition, we will preliminarily explore the extent to which this relationship works through several possible mediators, as detailed above. A multiple mediator analysis, which examines the effects of the potential mediators simultaneously in the same statistical model and is consistent with Baron and Kenny as updated by Kraemer^{69,70}, will be used to quantify the magnitude of the mediation.

Moderator analysis. To preliminarily explore effect modification, we will add interaction terms one-by-one for the intervention condition and the potential moderators. Significant or large interaction terms suggest that the effects of the intervention differ for different subgroups, as defined by the moderators.

For the mediation and moderator analyses, given the aim of the study is to pilot the intervention to assess participant acceptability and determine feasibility of all study procedures, we will assess whether the intervention impacts the hypothesized mediators and moderators in the expected direction per our conceptual model, not rely on statistical significance.

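### The indirect-effect (mediation) analysis runs only after a significant adherence result, and 'expected direction' or 'large' cannot separate a mechanism or subgroup effect from chance

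*SAP*

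**What the plan says.** Three statements in the SAP bear on this point.

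- **Mediation analysis.** The multiple-mediator model is introduced by a condition: "If the intervention does achieve adherence in significantly greater magnitude than the comparison condition". It then covers "several possible mediators, as detailed above".
- **Moderator analysis.** There is no such condition: "we will add interaction terms one-by-one for the intervention condition and the potential moderators". The reading rule is "Significant or large interaction terms suggest that the effects of the intervention differ for different subgroups". No threshold for 'large' is given.
- **Closing paragraph on both analyses.** Because this is a pilot, the team will look at whether the intervention affects the hypothesised mediators and moderators "in the expected direction per our conceptual model, not rely on statistical significance".

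Two other places set the context. Primary Analysis states "All analyses will use two-tailed tests of significance, with significance at alpha = 0.05", so I read the condition as p < 0.05 in favour of the intervention. Power and Sample Size Considerations says that power is limited and that only large effects would reach significance.

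**The concern.** The SAP's reason for not leaning on p-values in the secondary analyses is that the study is a small pilot. That reason applies equally to the condition placed in front of the mediation model, yet there a p-value decides whether the model is fitted at all.

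Two things are at stake. First, indirect effects may go unestimated when the intervention works, and when they are estimated it is in the samples where the adherence effect came out too large. Second, the criteria that do not use significance are a sign and an undefined notion of 'large'. Neither carries a measure of uncertainty, so a reader cannot tell a real mechanism or subgroup difference from noise.

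**Working it through.** **Inputs from the documents.** Stage 2 has 22 per arm and 40 completers, so 20 per arm (Protocol, Specific Aim 1). The correlation between repeated adherence measures is 0.80, with up to 10% attrition and three measures at baseline, 3 and 6 months (SAP, Power and Sample Size Considerations). Alpha is 0.05 two-sided. The primary contrast is described thus: "the primary analysis will compare adherence (defined by percent of drug in blood) at the 3 and 6 month visits between the study arms".

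**Assumptions of mine.** Compound symmetry; a true effect d = 0.5 SD; a binary moderator split 50:50; cuts of 0.5 and 0.8 SD for 'large'; illustrative numbers of mediators. Normal approximations throughout.

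**1. The plan's own figure.** With three equally spaced measures, the total change over the slope has variance 2(1 − 0.80) = 0.40 SD². With 20 per arm, SE = √(0.40 × 2/20) = 0.20. Power of 80% needs d = (1.96 + 0.84) × 0.20 = 0.56. This fits the SAP's claim of over 80% power for more than a medium effect, so the slope claim reproduces.

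**2. How often the condition blocks the analysis.** The SAP does not say which contrast opens the gate, so three are shown. SE = √(V × 2/20), where V is the per-person variance.

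- Unadjusted mean of months 3 and 6: V = (1 + 0.80)/2 = 0.90.
- Slope: V = 0.40, with d taken as total change.
- Baseline-adjusted mean of months 3 and 6: V = 0.90 − 0.80² = 0.26.

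Power = 1 − Φ(k), with k = 1.96 − d/SE.

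**3. Overstatement when it runs.** The mean of the significant positive estimates is d + SE × φ(k)/(1 − Φ(k)), which is then divided by d.

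| Contrast | SE | k | Power | Skipped | Overstatement |
|---|---|---|---|---|---|
| Unadjusted mean | 0.30 | 0.29 | 38% | 62% | 1.60 |
| Slope | 0.20 | −0.54 | 71% | 29% | 1.20 |
| Baseline-adjusted mean | 0.161 | −1.14 | 87% | 13% | 1.08 |

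At d = 0.8 even the unadjusted mean has 76% power and an overstatement of 1.15.

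**4. Why the condition is not needed.** In linear models the total effect is the direct effect plus the indirect effect, and the indirect effect is the product of the arm-to-mediator and mediator-to-outcome coefficients. Neither coefficient requires the total to be significant, and opposing paths can leave a small total beside a real indirect effect.

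**5. Expected direction.** With no effect and a symmetric estimate, each mediator passes with probability 0.5. At least one of three independent mediators passes with probability 1 − 0.5³ = 88% (75% by simulation if they are correlated at 0.5).

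**6. 'Large' interactions with no true interaction.** With 10 people per arm in each subgroup, SE = √V × √(2 × (1/10 + 1/10)) = √V × 0.632.

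| Contrast | SE | Beyond 0.5 SD | Beyond 0.8 SD |
|---|---|---|---|
| Unadjusted mean | 0.600 | 40% | 18% |
| Slope | 0.400 | 21% | 4.6% |
| Baseline-adjusted mean | 0.322 | 12% | 1.3% |

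**7. What intervals would show.** The 95% half-width is 1.96 × √(2/20) = 0.62 SD for an arm difference in a mediator. For an interaction it is 1.96 × 0.600 = 1.18 SD unadjusted, or 1.96 × 0.322 = 0.63 SD baseline-adjusted.

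**The case against.** The best defence has four parts.

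**The statements can be followed together.** The condition concerns the total effect on adherence; the closing paragraph concerns how effects on mediators and moderators are read. One may first ask whether there is an effect to explain, then read the mediators without p-values. This stands. A reader might infer that the SAP contradicts itself, but the text shows only an inconsistency of approach.

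**Mechanism is not lost altogether.** The closing paragraph has the team assess the arm's effect on mediators whatever the adherence result, and the moderator analysis has no gate. This also stands. What is gated is the step from mediator to adherence and the indirect effect.

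**The skip rate depends on the model.** A reader might infer that mediation will usually not be run. That holds only for the unadjusted mean of months 3 and 6. Under the slope for which the SAP claims power, or with baseline adjustment, the analysis runs in most trials with a true medium effect. Some caution is due on the favourable figures. Current Truvada users are excluded, and Stage 2 randomisation follows the clinic visit and prescription, so baseline drug level may predict later adherence less well than 0.80 implies. That is inference, and the SAP names no baseline-adjusted primary model.

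**The analyses are already labelled preliminary.** The SAP writes "To preliminarily explore effect modification", and its interaction rule only suggests differences. Nothing says that a chance subgroup will be carried into a later trial, and direction is not presented as a test. This limits the consequence. It does not supply a threshold or an interval, nor does it justify making estimation depend on a p-value.

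The mediator list is said to be detailed above and may lie in text not supplied, so its absence is not counted against the plan.

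**Conclusion.** The point holds as a minor one. Making the indirect-effect model conditional on a significant adherence result is unnecessary, sits badly with the SAP's own reasoning about a pilot, and inflates what is reported when the condition is met. For a true 0.5 SD effect the cost is a skipped analysis in about 13% to 62% of trials and a total effect overstated about 1.1- to 1.6-fold, depending on the contrast that opens the gate.

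The 50% chance rate for expected direction needs only symmetry under no effect. The rates for 'large' (about 12–40% at 0.5 SD, 1–18% at 0.8 SD) rest on assumed cuts, an even moderator split and compound symmetry; their spread reflects that the SAP fixes neither the cut nor the model.

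The point touches the interpretation of exploratory results only. The primary comparisons for Stage 1 and Stage 2 do not change.

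**What to change.** In the SAP:

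1. Delete the conditional clause and state that the mediation analysis is carried out whatever the p-value of the Stage 2 adherence comparison.
2. Report the arm-to-mediator, mediator-to-outcome and indirect effects, each with a 95% confidence interval. The interval method and the timing of mediator and outcome are for the team to choose, but should be written down in advance.
3. Report every interaction examined with its 95% confidence interval. Drop 'or large', and direction alone, as grounds for inferring a subgroup difference or a mechanism.
4. Keep the preliminary label.

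The cost is a few sentences and a small amount of analysis on data already being collected. The intervals will be wide, with a half-width of roughly 0.6 to 1.2 SD for an interaction, which shows openly how little a study of this size can say about subgroups.

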**Research Assessments:** Behavioral assessments will be conducted using ACASI at Stage 1 baseline, Stage 1 one-month follow-up, Stage 1 two-month follow-up, Stage 2 baseline, and Stage 2 three and six-month follow-up visits. It is expected that each ACASI survey will require less than 1 hour to complete. Both quantitative and qualitative assessment will collect information on the following key domains: sexual behavior; risk for HIV/STI transmission; use of alcohol and drugs; depression and anxiety; knowledge, attitudes, and beliefs related to pre-exposure prophylaxis. Exit interviews will be conducted as individual interviews and will last 15-20 minutes. Research assessments can be conducted at The Miriam Hospital, Brown University or Project Weber. Visits that include collection of blood and hair may only occur at The Miriam Hospital or Brown University. Participants who are unable to complete the Stage 2 three- or six-month follow-up visit in-person at Brown University or The Miriam Hospital may be given the option to schedule a phone interview with research staff to complete the Stage 2 follow-up assessment. This option will only be offered in extenuating circumstances (ex. participant moves out of the state). Phone interview follow-ups will be interviewer-administered. Participants who complete the phone interview will then receive instructions with a labeled, prepaid FedEx envelope to provide a self-collected hair sample. The sample will be mailed back to Brown University.

**Incentives:** All participants may receive up to \$210. Participants will receive \$30 USD compensation at each assessment visit (Stage 1 baseline, Stage 1 one-month follow up, Stage 1 two-month follow-up, Stage 2 baseline, Stage 2 three-month follow up and Stage 2 six-month follow up), individuals randomized to the strength based case management intervention condition will receive \$15 USD for the first case management session and individuals randomized to the Stage 2 intervention condition will also receive \$15 USD

compensation for each of the PrEPare for Work intervention sessions attended. Participants who complete a phone interview follow-up will receive a \$15 gift card upon completion of the interviewer-administered assessment and an additional \$15 gift card once the participant's hair sample is received via FedEx. Study staff will confirm the mailing address with participants prior to sending the gift cards.

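### The SAP judges its moderator analyses by a mediator criterion (whether the intervention changes the moderators) and does not restrict moderators to values recorded before randomisation

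*SAP*

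**What the plan says.** The SAP's moderator analysis paragraph opens with an exploratory purpose ("To preliminarily explore effect modification") and gives the method: "we will add interaction terms one-by-one for the intervention condition and the potential moderators". It then says how to read the result: "Significant or large interaction terms suggest that the effects of the intervention differ for different subgroups, as defined by the moderators".

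The next paragraph covers the mediation and moderator analyses together. Citing the pilot aim, it says "we will assess whether the intervention impacts the hypothesized mediators and moderators in the expected direction per our conceptual model", and adds that the study will "not rely on statistical significance".

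Neither document names a moderator or says at which visit moderators are taken. The SAP's pointer to a list given earlier concerns mediators, and no such list is in the text available. The Protocol, under Research Assessments, has ACASI surveys at Stage 1 baseline, one and two months, and at Stage 2 baseline, three and six months. Their domains include "use of alcohol and drugs; depression and anxiety". The SAP's Primary Analysis paragraph treats some behaviours as outcomes: "Changes in self-reported adherence, sexual behavior adjustment and substance use will also be examined".

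**The concern.** A moderator marks subgroups in which the arm effect on the outcome differs. A mediator is a variable through which arm acts, so arm must change it. The paragraph after the moderator analysis applies the second test to both kinds of variable.

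Two things follow. First, an analyst who follows that sentence would compare the moderators between arms and report the direction of the difference, which does not address effect modification. Second, asking whether the intervention changes a moderator makes sense only for a value measured after randomisation. If such values also define the subgroups, men with the same value are no longer comparable across arms, and the subgroup effects lose the protection of randomisation.

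At stake is the trial's preliminary account of who benefits, which a larger trial might use to choose its population or stratification factors. No primary result depends on it.

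**Working it through.** The documents give no figure for the moderator analysis, so there is none to reproduce. The check is a reading of the text followed by an illustration with assumed values.

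**1. The two paragraphs side by side.** Let A be arm, M the moderator and Y the outcome.

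- Moderator paragraph: the model has terms in A, M and A×M, and the quantity read is the A×M coefficient.
- Following paragraph: the quantity read is the difference in M between arms, E(M | A=1) − E(M | A=0).

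These are different quantities, and neither determines the other. If M is recorded before randomisation, the second is zero in expectation whatever the A×M coefficient is. If M is recorded afterwards, the second can be non-zero with no effect modification at all. The two paragraphs also differ on significance: the first counts a significant interaction as evidence, and the second sets significance aside.

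**2. Timing.** The behavioural domains are measured both before and after each randomisation, so both kinds of value will exist. Stage 2 baseline comes after Stage 1 randomisation, so the word baseline alone would not settle which value is meant.

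**3. What timing does to subgroup effects (all parameters assumed).** Let U be an unmeasured factor, standard normal, with Y = 0.5A + U + error. The true effect is then 0.50 in everyone and the true interaction is 0. M = 1 when a latent score L exceeds 0, and errors are standard normal. The effect seen in a subgroup is 0.50 + E(U | A=1, M) − E(U | A=0, M). For L with mean m and standard deviation s, writing c = cov(U, L)/s and t = m/s:

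- E(U | M=1) = c·φ(t)/Φ(t)
- E(U | M=0) = −c·φ(t)/(1 − Φ(t))

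*Control arm, and both arms if M is fixed before randomisation:* L = U + error, so c = 0.7071 and t = 0. The means of U are +0.564 and −0.564. With M fixed beforehand they cancel between arms, and the effects are 0.50 and 0.50.

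*Arm shifts L by 1:* c = 0.7071, t = 0.7071, φ = 0.3107, Φ = 0.7602. Prevalence of M=1 rises from 50% to 76%.
- M=1: 0.50 + 0.289 − 0.564 = 0.22
- M=0: 0.50 − 0.916 + 0.564 = 0.15
- False interaction: 0.289 − 0.564 + 0.916 − 0.564 = 0.08

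*The shift also depends on U:* L = 2U + 1 + error in the intervention arm, so c = 0.8944, t = 0.4472, φ = 0.3610, Φ = 0.6726.
- M=1: 0.50 + 0.480 − 0.564 = 0.42
- M=0: 0.50 − 0.986 + 0.564 = 0.08
- False interaction: 0.34

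Simulation with 2,000,000 subjects gives 0.22 and 0.15 (interaction 0.07) for the first shift, and 0.41 and 0.08 (interaction 0.33) for the second.

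**4. A case where the interaction is not biased.** Take a continuous moderator with M = 0.6·M0 + 0.5A + uU + error and Y = 0.25A + 0.5M + uU + error. The total arm effect is 0.25 + 0.5 × 0.5 = 0.50. In the model with follow-up M and A×M, the interaction is 0.00 for u = 0 and u = 0.4, which is correct. The arm coefficient is 0.50 − 0.5 × slope, where slope = 0.5 + u²/var(M within arm):

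- u = 0: 0.50 − 0.5 × 0.50 = 0.25, which is the direct effect.
- u = 0.4, within-arm variance 1: 0.50 − 0.5 × 0.66 = 0.17.
- u = 0.4, residual SD 1 (variance 0.36 + 0.16 + 1 = 1.52): 0.50 − 0.5 × 0.605 = 0.20.

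With the baseline value M0 in the model, the arm coefficient is 0.50. Whether the interaction itself is distorted therefore depends on the assumed mechanism.

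**5. Precision.** With 20 Stage 2 completers per arm (Protocol, Specific Aim 1), an assumed even split on the moderator, one continuous measure and two-sided alpha of 0.05, the standard error of the interaction is √(4/10) = 0.632 SD. The interaction detectable with 80% power is (1.96 + 0.84) × 0.632 ≈ 1.8 SD, against (1.96 + 0.84) × √(2/20) ≈ 0.9 SD for the main effect. This is a separate limit on the analysis. It supports reporting estimates with intervals.

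**The case against.** The strongest reply is that the stated moderator analysis is the interaction model, and that model is sound. On this view the later sentence is shorthand: in a pilot, mediation paths and interactions will be judged by direction. Nothing says that follow-up values will define moderators, and measuring a variable repeatedly does not mean its later values will be used. An arm effect on a later measurement does not spoil subgroups defined by the earlier one. The moderators may be defined in material not included here.

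Most of this stands. A reader might infer that the moderator analysis cannot show for whom the intervention works, or that its results will be biased. The documents do not support either inference: the interaction model is valid with pre-randomisation values, and no passage rules those out. Nor do they identify substance use or depression as moderators; these are only plausible candidates. The model in step 4 shows that even post-randomisation values need not distort the interaction, and the SAP does not propose to read the arm effect from that model.

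The shorthand reading does not remove the point. The sentence names the intervention's impact on the moderators as what will be assessed. Reading it as the direction of the interactions needs words it does not contain.

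**Conclusion.** The concern holds in a limited form. The SAP states a wrong criterion for moderators: it does not test effect modification, and it conflicts with the interaction approach in the paragraph before it. By implying that moderators may be variables the intervention changes, without requiring pre-randomisation values, the SAP leaves room for an analysis that could mislead.

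The size of any bias cannot be derived from the documents. Under the assumed parameters it ranges from no error in the interaction to a false interaction of about 0.34 when the truth is zero. It arises only if post-randomisation values are used.

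Severity is low: the analysis is exploratory, the trial is a pilot, and no primary comparison or sample size rests on it.

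**What to change.** Three changes to the SAP text:

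1. Limit the sentence about the intervention's impact to mediators.
2. State that moderators use only values recorded before the randomisation being analysed: Stage 1 baseline for Stage 1, and Stage 2 baseline or earlier for Stage 2, provided that assessment is completed before Stage 2 allocation. Naming the moderators in the same place would close the remaining gap.
3. State that moderation is judged by the direction and size of each arm-by-moderator interaction estimate with its 95% CI, labelled exploratory. This replaces the reference to significant interactions and agrees with the plan not to rely on significance.

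The cost is a few sentences. Baseline assessments are already scheduled in both stages, so no new data, visits or participants are needed, and sample size and power do not change.

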## RESEARCH PROTOCOL

**Specific Aim 1 - Pilot RCT:** To evaluate both PrEP initiation and adherence, we will use a two-stage randomization design. In Stage 1, we plan to enroll 130 MSW (65 per randomization arm to achieve N=104 completers for Stage 1; ~80% retention), who will be equally randomized to receive either the PrEPare for Work strength-based case management (SBCM) or standard of care (i.e., referrals only) to evaluate successful PrEP initiation. In Stage 2, those who initiate PrEP (n~44; ~80% in Stage 1 intervention arm and ~20% in Stage 1 comparison arm), regardless of their Stage 1 randomization condition, will then be equally randomized to the PrEPare for Work adherence intervention condition or standard of care comparison condition (22 per randomization arm to achieve N=40 completers for Stage 2; ~90% retention). While we are aware that there may be important differences that affect adherence in those who initiate PrEP without additional SBCM and those who received SBCM, we anticipate that randomization at the second stage will balance out potential confounding by level of motivation to initiate PrEP. See point of contact diagram below for specific details.

**Recruitment:** All participants will be identified by staff at Project Weber, our community partner organization and study site for this study, and will live in or participate in sex work in RI. In addition to identifying participants at the drop-in center, participants will be recruited from a variety of sources: (1) members of our recruitment/outreach team will actively recruit participants in the community via direct outreach at venues where we know sex workers solicit clients (such as bars, night/dance clubs, on the streets), (2) via the internet, by posting study related advertisements which may include a brief anonymous self-administered pre-eligibility assessment, (3) via direct engagement with internet escorts on the internet for which

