Power and Sample Size Considerations. As a pilot study, the primary emphasis is on feasibility of the two arms and hence power is limited; and to find statistical significance, the effect sizes would need to be large. However, the number of repeated measures does increase power for the longitudinal analyses. For stage 1, proportion of participants in each condition who initiate PrEP, with a two-tailed p-value of 0.05, and 53 participants per arm, we would need at least a 30 percentage point difference across the two conditions (e.g., if 20% of the comparison arm and 50% of the intervention arm initiated PrEP) to achieve 80% power. For stage 2, percent adherence since the last visit will be assessed yielding 3 repeated blood-drug levels across baseline, 3, and 6. With a two-tailed p-value of 0.05, group sample sizes of 22 participants per arm, assuming a correlation of 0.80 between repeated adherence measures and with up to 10% attrition there will be greater than 80% power to detect in excess of a medium effect size difference (approximately 10% in the slope) between the intervention and comparison groups. For categorical outcomes (e.g. percent of patients in each condition achieving at least 90% adherence via blood drug levels), with a two-tailed p-value of 0.05, the three repeated measures, and 22 patients per arm, we would need at least a 25 percentage point difference across the two conditions (e.g., if 50% of the comparison arm and 75% of the intervention arm had at least 90% adherence) to achieve 80% power.

Missing Data. We will assess for patterns of missing data, which are expected to be low as the study utilizes A-CASI. We will explore strategies for imputing missing data based on patterns of missingness and apply appropriate techniques, applying sensitivity analysis to determine the optimal method of handling the missingness⁷¹⁻⁷³.

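### The SAP's Stage 1 power statement is wrong for its own example: 20% vs 50% with 53 per arm has about 87–91% power, not 80%

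*SAP*

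**What the plan says.** The SAP, under Primary Analysis, sets the Stage 1 comparison at one time point: "The primary analysis for Stage 1 will compare PrEP initiation at 1-month post Stage 1 randomization between the study arms". It also fixes the error rate: "All analyses will use two-tailed tests of significance, with significance at alpha = 0.05".

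Under Power and Sample Size Considerations it states that "with a two-tailed p-value of 0.05, and 53 participants per arm, we would need at least a 30 percentage point difference" for 80% power. The accompanying example is "if 20% of the comparison arm and 50% of the intervention arm initiated PrEP". For Stage 1 it names no test, continuity correction or attrition allowance, whereas the Stage 2 sentence that follows does mention up to 10% attrition.

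The protocol, under Specific Aim 1, gives equal randomization and the planned numbers: "65 per randomization arm to achieve N=104 completers for Stage 1; ~80% retention". It then describes entry to Stage 2 as "those who initiate PrEP (n~44; ~80% in Stage 1 intervention arm and ~20% in Stage 1 comparison arm".

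**The concern.** The outcome type, time point, allocation, sample size, significance level and both rates are all given, so only the choice of test is open. A difference of 20% versus 50% is large for 53 per arm, and 80% looks too low for it.

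The direction matters. A misstatement that overstated power would put the trial at risk; this one understates it. What is at stake is interpretation. A reader would take a true difference of 26 to 28 points as below the 80% power threshold when, from a 20% base, it is at or close to it. Anyone planning a follow-on study in the same way would also enrol more than 20% versus 50% requires.

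**Working it through.** **Inputs**

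- Comparison arm 20%, intervention arm 50%, 53 per arm, target power 80% (SAP, Power and Sample Size Considerations).
- Two-sided 0.05, so z = 1.96 (SAP, Primary Analysis).
- One binary observation per person at one month (SAP, Primary Analysis).
- Equal allocation; 65 randomized per arm, 104 completers, so 104/2 = 52 per arm (Protocol, Specific Aim 1).

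**Step 1. Try to reproduce the SAP's 80%.** With p1 = 0.20, p2 = 0.50 and mean p = 0.35, the pooled z approximation is

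power = Φ{ [d − 1.96·√(2·p(1−p)/n)] / √([p1(1−p1) + p2(1−p2)]/n) }.

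- Null standard error: √(2 × 0.35 × 0.65/53) = √(0.455/53) = 0.0927; × 1.96 = 0.1816.
- Alternative standard error: √((0.16 + 0.25)/53) = √(0.41/53) = 0.0880.
- Pooled z: (0.30 − 0.1816)/0.0880 = 1.346, so power is **91.1%**.
- Continuity-corrected: replace d by 0.30 − 1/53 = 0.2811. Then (0.2811 − 0.1816)/0.0880 = 1.132, so power is **87.1%**.
- Fisher's exact test, by enumerating all outcomes: **87.8%**.

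Other standard choices do not come nearer to 80%: unpooled z 92.7%, arcsine 91.2%, exact power of the Pearson test 91.6%, log-odds-ratio Wald 88.3%, exact power of the Yates test 87.8%. The stated 80% is not reproduced.

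**Step 2. Sample size that does give 80% for 20% versus 50%.**

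- Pooled z: n = [1.96·√0.455 + 0.8416·√0.41]² / 0.30² = (1.3221 + 0.5389)²/0.09 = 38.5, so 39 per arm.
- Continuity-corrected: 45 per arm.
- Fisher: 44 per arm.

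**Step 3. Difference that gives 80% power.** The power expressions in Step 1 were solved numerically for the intervention-arm rate, first from a 20% base and then over bases from 5% to 65%.

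| | Pooled z | Corrected | Fisher |
|---|---|---|---|
| 53 per arm, from 20% | 25.2 points | 27.3 | 27.0 |
| 53 per arm, largest over all bases | 26.9 | 28.8 | 29.2 |
| 52 per arm, from 20% | 25.5 | 27.6 | 27.4 |

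The least favourable base is about 36%. Even 30 points placed symmetrically around one half (35% versus 65%, 53 per arm) has 88.2%, 83.6% and 82.3% power respectively.

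**Step 4. 53 or 52 per arm.** With 52 per arm, 20% versus 50% has 90.6%, 86.4% and 86.9% power. The one-person gap changes power by 0.5 to 0.9 points, so it does not explain the discrepancy.

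**Step 5. The protocol's 80%/20% phrase (a clarification, separate from the power error).**

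- Read as the make-up of the 44 Stage 2 entrants: 0.8 × 44 = 35.2 and 0.2 × 44 = 8.8, about 35 + 9. That is 68% and 17% of 52 completers per arm, or 54% and 14% of 65 randomized per arm.
- Read as initiation rates within each arm: 52 × (0.8 + 0.2) = 52, or 65 × (0.8 + 0.2) = 65. Neither is 44.

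**The case against.** Four points can be made for the SAP.

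**It may be a rounded worst case.** The 30 points are stated generally and the 20%/50% pair is only an example. With the base rate left open, the largest required difference is 28.8 (corrected) or 29.2 (Fisher), which a planner might round to 30. That would shrink the gap to about one point. But the SAP does not say it is quoting a worst case, and it ties 80% power to a pair of rates for which power is 7 to 11 points higher.

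**An unstated attrition allowance may explain it.** About 44 to 45 evaluable per arm gives 80.2% (Fisher, 44) or 80.1% (corrected, 45), a loss of roughly 15–17% from 53. The SAP (2015) predates this protocol version (2018), so an undocumented allowance cannot be excluded. However, 53 is already about the protocol's completer number, so a further loss would count attrition twice. If an allowance was used, the SAP still has to state it.

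**It has little consequence.** This stands. It is a pilot, the SAP says power is limited and effects would need to be large, and 25 to 29 points is still large. A completed Stage 1 would also be read mainly from its estimate and confidence interval.

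**The side issues are small.** This also stands. Both 53/65 = 81.5% and 52/65 = 80% fit retention of about 80%, and the 80%/20% phrase concerns Stage 2 entry. Neither adds weight to the main point.

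**Conclusion.** The Stage 1 power statement is wrong as written. Stated: 80% power and a minimum of 30 points. Computed at 53 per arm: 87–91% power for the SAP's own example, and 25–27 points from its own 20% base, or at most about 29 points from any base. These ranges cover the pooled z, continuity-corrected and Fisher tests; the unpooled z test lies slightly further from the SAP's figures.

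The result assumes that 53 is the number per arm analysed, with no further loss, and that the comparison is the single one-month binary outcome the SAP describes. The SAP's remark that repeated measures add power concerns its longitudinal analyses and does not apply to that comparison.

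Confidence in the arithmetic is high. Its practical importance is modest, because the error is conservative and does not threaten the sample size.

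**What to change.** Recalculate the Stage 1 sentence, name the test, and state whether any attrition is allowed for beyond the number quoted. Suggested content: with 52 completers per arm and a two-sided 0.05 test, 80% power for a difference of about 26 to 28 points from a 20% base, and about 86–91% power for 20% versus 50%. Once the test is chosen, replace each range with its single value. Use 52 per arm to match the protocol, or explain 53.

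As a minor addition, the protocol's Specific Aim 1 should say whether the 80%/20% figures describe the make-up of the roughly 44 Stage 2 entrants or the initiation rates within each arm, and from which base (completers or all randomized) 44 was derived.

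The cost is one recalculation, a reworded SAP sentence and a clarifying phrase in the protocol. Enrolment and analysis do not change.
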